## **5.2. Database lock**

After completion of all BDR procedures, validation of the project databases and Regency's approval of the BDR, the clinical database will be locked. After the database lock and the authorization for unblinding, the treatment codes will be merged to the analysis datasets. After database lock, final endpoint analysis may commence. Note that there will be two separate database locks that follow soft locks and data reviews; one after the randomized control period has completed and one after the Week 28 follow-up period has completed.

## **5.3. Authorization for unblinding**

The fire-walled unblinded analysis team at Medpace will have access to the treatment codes for analysis purposes. After database lock, top-line results will be available to Regency.

## 6. Statistical analyses

Statistical analyses will be performed using SAS® software version 9.4 or later.

### 6.1. Statistical methodology

#### 6.1.1. Sample size determination

The sample size for this study is planned to be approximately 274 evaluable patients. This sample size provides 80% power to detect a treatment difference of 0.8 points on the NRS. Assuming a pooled standard deviation of 2.35, this corresponds to a standardized effect size of approximately 0.34.

#### 6.1.2. Analysis populations

The following populations are planned:

- Pre-randomized safety population (pSAF): All patients who have at least one observation during the pain observation period (day -14 to day -1/pre-treatment) and who were not randomized.
- Safety population (SAF): All patients who been randomized and received at least one dose of study drug
- Intent to treat (ITT) population: All patients randomized regardless of study drug administration
- Full analysis set (FAS) population: All patients who receive at least one dose of study drug, have a baseline average NRS score and, have at least one post-baseline average NRS score.
- Per-protocol population (PPP): All patients in the FAS population who have no major protocol violations, a valid baseline value of the NRS, meet all inclusion/exclusion criteria, missing no more than 2 weeks of diary data, and have a mean compliance rate of at least 60% (i.e., on average provide ratings on 4 or more days of each week).

6.1.3. *General considerations*

When presented, listings will be presented by patient number, treatment group, and measurement time.

In all analyses, the same number of decimal places as in the raw data will be presented for point estimates and univariate analysis. One more decimal place than in the raw data will be presented when reporting mean and standard deviation.

Continuous variables will be summarized by treatment group using descriptive statistics (n, mean, median, standard deviation, minimum, and maximum). For categorical variables, frequencies and percentages will be presented by treatment. The denominator for all categorical variables is the number of randomized patients.

All statistical testing will be based on a two-sided significance level of 0.05 unless otherwise stated.

*Baseline* is defined as the last observation prior to initiation of study medication.

Baseline assessment for the NRS is expected to be the mean of the values collected during the 5-9 days that 1) follow the training visit follow-up assessment at the end of the first week of the pain observation phase and 2) immediately precede randomization (i.e., prior to the initial study drug dose administration). Should this value be unavailable (for example, if less than 5 days were present between the training visit follow-up visit and randomization) or should the timing of the evaluation in relation to the first administration of study drug not be determinable (e.g., missing time for baseline assessment or missing time value for study drug administration) then the mean of the 5 days of the NRS ratings closest to and before randomization will be selected as the baseline value. Instead of relying solely on visit labels in the clinical database for post-baseline values, results collected at a particular time will be attributed to a specific time point by calculating the time relative to randomization.

For all other assessments, the baseline assessment is the last value for that assessment collected prior to randomization and the first administration of study drug.

For visits (or events) that occur on or after randomization, study day is defined as:

$$\text{Study day} = \text{date of event} - \text{randomization date} + 1$$

For visits (or events) that occur before randomization, study day is defined as:

$$\text{Study day} = \text{date of event} - \text{randomization date}$$

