## **9.6 Safety Extension (Week 12 to Week 24)**

From Week 12 to Week 24, all patients will receive ricolinostat 120 mg daily. Patients will return to the clinic as outlined in the schedule of events and at each visit procedures specified in the schedule of events for that visit will be performed.

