### 10.3.3 Primary Efficacy Outcome Measures

The null hypothesis is that there is no difference between the average change from baseline in the NRS score in the ricolinostat and placebo groups; the null hypothesis is stated as  $H_0: \Delta_R = \Delta_P$ , where  $\Delta_R$  denotes the average change from baseline in the NRS score in the ricolinostat group and  $\Delta_P$  denotes the average change from baseline in the NRS score in the placebo group. The alternative hypothesis is stated as  $H_A: \Delta_R \neq \Delta_P$  with a two-sided significance level of 0.05.

The primary estimand for this study is defined by the following attributes:

Estimand attribute	Description
Population	Full analysis set population, which consists of all patients who receive at least one dose of study drug and have baseline average pain intensity score and at least one post-baseline average pain intensity score.
Endpoint	Weekly mean of daily average pain based on the 11-point NRS.
Intercurrent events	All observations in patients who are on stable permitted concomitant pain medication for DPN and who started at least 3 months prior to Screening will be included. If there is a dose change, pain scores after the dose change will be considered missing and will be imputed using Medical Administration Record (MAR) assumption.
Summary measure	Difference between ricolinostat arm and placebo arm as measured by change from baseline in average pain at Week 12.

The primary estimand is the difference in the mean change from baseline through Week 12 in the average pain as measured by the NRS. Patients will record their average pain and worst pain on a daily basis in a diary starting seven days prior to randomization through the end of the study using the NRS, where 0 represents no pain and 10 represents worst possible pain. The baseline average pain score is the mean of the average daily pain scores recorded from day -7 to -1 of the study. (Note: For visits prior to randomization, study day=visit date-randomization date. For visits after randomization, study day=visit date-randomization date+1.) The weekly mean of the average pain will be calculated when four or more daily average pain scores exist for that week. If a patient has fewer than four daily average pain scores in a week, then the weekly mean pain will be set to missing for that week.

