If a site closes or a patient resides in a location where a shelter-in-place order is issued, the Investigator must consult with the Medical Monitor to determine the best course of action, particularly for those patients who have not yet completed the baseline visit. For patients that have completed the baseline visit, remote visit activities can proceed as outlined in [Table 3](#). A combination of home health visit and telemedicine activities may be used. If in-clinic visits are no longer possible, activities categorized as in-clinic-only activities will not be conducted. If the shelter-in-place order is lifted after a missed clinic visit, attempts should be made to conduct the missed in-clinic-only activities via an unscheduled visit.

If a patient or a member of the patient's household is suspected or confirmed to have COVID-19, the Investigator must consult with the Medical Monitor to determine the best course of action. In this situation, only telemedicine activities can proceed. If the patient misses in-clinic visits during this time, an unscheduled visit will be conducted once the patient or member of his/her

household no longer has suspected or confirmed COVID-19. At a minimum, safety labs must be performed at the unscheduled visit. Patients cannot go more than 12 weeks or 2 consecutive visits without labs being drawn.

For scenarios not delineated here or for further clarification, the Investigator should consult the Medical Monitor to determine the best course of action.

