## 5. **Database lock and unblinding**

### 5.1. **Blinded data review (BDR) review of selected data prior to database lock**

The clinical database will undergo a “soft lock” when the last patient that is still in the randomized control period has completed their Week 12 visit or early study discontinuation. During the soft lock, all variables will be locked for changes except for those variables that will continue collection during the 12-week open label period (e.g., adverse events, laboratory assessments, IENFD, etc.); the data from these variables will be locked for all records collected

prior to and through the Week 12 visit. To avoid inadvertent unblinding, any data collected after Week 12 during the open label period will remain unlocked, excluded from analysis, and blinded with respect to treatment group assignment.

After the soft lock and prior to accessing the randomized treatment assignments, a review of locked blinded data will occur to accomplish the following objectives: 1) assess the impact of missing data on study analysis, 2) assess and correct the database for inconsistent data, 3) identify the per-protocol population and, 3) finalize the methods needed for analysis of the study objectives while still blinded to results. Outputs consisting of tables, listing, and figures without treatment groups or with randomly generated treatment group assignments will be produced, as needed, to accomplish the blinded data review.

A second (unblinded) data review may occur after the final patient has completed the Week 28 visit or early study discontinuation. The data collected after the initial soft lock will be analyzed during the second data review. The procedures and objectives for this data review are the same as those described above after study completion of the randomized control period.

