**Exhibit 4. Example of study days and analysis timepoints**

Analysis visit	Label	Study day a	Analysis window
0	Day 1 b	1	1
1	Week 1	5	2 ≤ study day ≤ 9
2	Week 2	14	10 ≤ study day ≤ 18
4	Week 4	28	24 ≤ study day ≤ 32
8	Week 8 c	56	52 ≤ study day ≤ 60
12	Week 12 d	84	14 ≤ days after last dose ≤ 32
14	Week 14	98	94 ≤ study day ≤ 102
18	Week 18	126	122 ≤ study day ≤ 130
24	Week 24 e	168	164 ≤ study day ≤ 172
26	Week 26 f	182	14 ≤ days after last dose ≤ 32
28	Week 28	196	192 ≤ study day ≤ 200

a) Study Day is relative to the date of randomization (Section 6.1.3).

b) Day 1 is the last measurement prior to the first study drug administration.

c) Week 8 is the end of the double-blind, placebo-controlled treatment period.

d) Week 12 is the start of the open-label safety extension period.

e) Week 24 is the end of the open-label safety extension period.

f) Week 26 is the start of the follow-up period.

*6.1.5. Procedures for handling missing data*

*6.1.5.1. Missing data on the primary efficacy endpoint*

The primary efficacy endpoint (e.g., NRS) is captured in a daily log. Missing daily NRS entries will be handled by performing a simple weekly average of the daily scores so long as four or more entries occur during the week. If three or fewer entries occur during the week, then the scores' weekly average will be set to missing for that week. Missing values will be multiple imputed using missing at random multiple imputation for intermittent missing values and reference-based imputation for all other missing data. These data will be part of the blinded data review with the option to change the approach to the summary score during the blinded data review process.

*6.1.5.2. Missing UENS*

The key secondary endpoint will be analyzed using missing at random imputation for intermittent missing data and reference-based imputation for all other missing data.

*6.1.5.3. Missing data for secondary endpoint*

Missing values for secondary endpoints will not be imputed. All results will be analyzed under the complete case scenario.

*6.1.5.4. Missing or partial stop- or start-dates for adverse events*

Missing or partial stop- or start-dates for adverse events will be imputed using the most conservative (e.g., worst case scenario) assumption. In all cases of missing or partial information, the site will be instructed to attempt to obtain the missing details. The rules for imputation follow:

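### The SAP does not end the Week 12 pain mean at the switch to open-label drug, so some primary-endpoint ratings may be made on open-label ricolinostat

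*SAP*

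**What the plan says.** **Timing of the switch.** Protocol Table 1 gives the Week 12 visit a window of Day 82 to Day 86. Protocol 9.6 states: "From Week 12 to Week 24, all patients will receive ricolinostat 120 mg daily". Protocol 9.6.1 lists dispensing of study drug among the Week 12 procedures. It does not say whether the first open-label dose is taken that day or the next morning. SAP Exhibit 4, footnote d, labels Week 12 as the start of the open-label period.

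**Attribution of ratings.** Protocol 10.3.3 has the daily diary run to the end of the study. For post-baseline values SAP 6.1.3 says that "results collected at a particular time will be attributed to a specific time point by calculating the time relative to randomization", and SAP 6.1.4 says that windows use derived study day. SAP 6.1.5.1 averages the daily scores "so long as four or more entries occur during the week". The days that make up a diary week are given only for Week 4 (Days 22 to 28, Protocol 10.2.1.1.1).

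**Exhibit 4.** The Week 12 row has a target of Day 84, but its window is 14 to 32 days after last dose, not a range of study days.

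**Data lock.** SAP 5.1 locks continuing variables through the Week 12 visit and adds that "any data collected after Week 12 during the open label period will remain unlocked, excluded from analysis".

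**UENS.** Protocol Table 3 makes UENS an in-clinic activity, while study drug may be shipped to the patient. After a visit missed for COVID-19 reasons, Protocol 13.2 says that "attempts should be made to conduct the missed in-clinic-only activities via an unscheduled visit".

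**The concern.** The SAP ties the baseline pain score to the period before the first dose of study drug, but has no matching anchor at the end of blinded treatment. Under study-day attribution, a placebo patient seen early in the visit window can contribute Week 12 ratings made on ricolinostat, knowing that it is ricolinostat. The start of open-label drug is not among the intercurrent events in SAP Table 1.

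There is some reason to think that a few days could matter. Protocol 5.3 reports an effect in rats after the first dose, and Protocol 5.5 recognises that pain ratings respond to expectation. If placebo patients improve in those days, the Week 12 difference shrinks. If the diary is instead cut at the visit, early-visit patients have fewer days from which to reach four ratings. Two programmers could derive different Week 12 values from the same data.

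**Working it through.** **1. The plan's own figure.** Inputs: test "with a two-sided significance level of 0.05" (Protocol 10.3.3); "This sample size provides 80% power to detect a treatment difference of 0.8 points on the NRS" and "Assuming a pooled standard deviation of 2.35" (SAP 6.1.1); 274 evaluable patients at 1:1, so 137 per arm.

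- SE = 2.35 × √(2/137) = 0.284.
- Power = Φ(0.8/0.284 − 1.96) = 80.4%. A two-sample t-test needs 137 per arm, which is 274. The sample size reproduces.

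**2. Exposed ratings.** Assumption: diary Week 12 is Days 78–84, by analogy with Days 22–28 for Week 4. The count is of days on or after the first open-label dose.

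| Visit day | 82 | 83 | 84 | 85 | 86 | Mean share if visits are uniform |
|---|---|---|---|---|---|---|
| First dose on visit day | 3/7 | 2/7 | 1/7 | 0 | 0 | (6/5)/7 = 17.1% |
| First dose next morning | 2/7 | 1/7 | 0 | 0 | 0 | (3/5)/7 = 8.6% |

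Uniform visits over Days 82–86 are an assumption; the documents give no distribution.

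**3. Effect on power.** Diluted difference = 0.8 × (1 − f × e), where f is the exposed share and e is the fraction of the full drug effect that placebo patients reach in those first days. The SD and sample size are unchanged.

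| e | Same-day dose: difference, power | Next-day dose: difference, power |
|---|---|---|
| 1 (upper bound) | 0.66, 64.6% | 0.73, 73.1% |
| 0.5 | 0.73, 73.1% | 0.77, 76.9% |
| 0.25 | 0.77, 76.9% | 0.78, 78.7% |
| 0 | 0.80, 80.4% | 0.80, 80.4% |

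**4. If SAP 5.1 cuts the diary at the visit.** At most the visit-day rating is then exposed, and none if dosing starts the next morning. A Day 82 patient keeps Days 78–82 (five days), or four if the visit-day rating is also dropped. At an assumed 85% daily compliance, the binomial chance of at least four ratings is 99% with seven days, 84% with five and 52% with four. With the visit day kept and visits uniform, the average is about (84 + 95 + 99 + 99 + 99)/5 = 95%.

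**5. Exhibit 4.** The earliest last double-blind dose for a patient who completes the blinded period is about Day 81 (visit on Day 82, open-label dose that day). Then 81 + 14 = Day 95 and 81 + 32 = Day 113. Read from the last double-blind dose, the Week 12 window lies wholly in the open-label period and does not contain its own Day 84 target.

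**The case against.** The strongest reply is SAP 5.1. The diary continues past Week 12, so it is a continuing variable, and the lock is worded by the visit. On that reading most exposed ratings never reach the primary analysis. This largely stands. However, the exclusion sentence refers to data after Week 12 without saying whether that is the visit or the study week, and a locking rule is not linked to the derivation of the weekly mean. The visit reading also shortens the diary week for early visits, though the loss is modest on average and missing means are imputed.

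Other points also stand. The attribution sentence in 6.1.3 opens by saying that visit labels will not be the only basis, so it does not discard them. Days 78–84 is an inference. In-clinic dosing is specified only for Day 1, so a next-morning first dose is plausible. Both arms know that they are on active drug after the switch, so a shared expectation effect would partly cancel. SAP 6.1.5.1 lets the summary-score approach change at the blinded review, but that option is not a rule.

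A reader might infer that the plan directs contaminated ratings into the primary endpoint and that power is really about 65%. The documents do not support that. The 65% needs study-day attribution with 5.1 ignored, same-day dosing, and the full drug effect on the first open-label day. Protocol 7.2 says that full effect in patients could take longer.

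A reader might also infer that UENS is routinely exposed. The shipped-drug and catch-up route is a COVID-19 contingency of unknown frequency, and the Exhibit 4 window for that visit is not by study day. What remains is that no rule bars a catch-up UENS taken on open-label drug from counting as Week 12.

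**Conclusion.** The gap is real but limited. The days that form the primary-endpoint week are undefined at the point where treatment changes, and three parts of the SAP point different ways: study-day attribution in 6.1.3 and 6.1.4, the days-after-last-dose window in Exhibit 4, and the lock in 5.1.

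Under Days 78–84, only visits on Days 82–84 are affected with a same-day first dose (one to three of seven ratings), or on Days 82–83 with a next-day dose (one or two of seven). With uniform visits, the cost ranges from nothing (no early effect), through power of 77–79% (a quarter of the effect), to an upper bound of 65–73% (full effect at once). The documents do not give speed of onset in patients, so the position within that range is unknown.

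If the drug works, the bias is toward no difference. If it does not, exposed ratings give no reason to expect a false difference, so type I error is not inflated. The sample size calculation is not in error. This should be fixed before unblinding, as a clarification of the primary endpoint rather than a defect that undermines the trial.

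**What to change.** 1. In SAP 6.1.3 and 6.1.5.1, define the Week 12 NRS mean (average and worst pain) as Days 78–84. If the first open-label dose falls on or before Day 84, use instead the last seven diary days before that dose. Require at least four ratings in either case. Patients who never take an open-label dose keep Days 78–84, so post-discontinuation values still count as SAP Table 1 intends. Take the dose date from the daily dosing diary and dispensing records.
2. Replace the Week 12 window in Exhibit 4 with a study-day window that ends before the first open-label dose.
3. State that Week 12 in SAP 5.1 means that same cut-off.
4. State that no UENS or other efficacy value collected after the first open-label dose is used as a Week 12 value. List a late catch-up UENS and treat it as missing under 6.1.5.2.

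The result is no exposed ratings, a full seven-day week for every visit day, and no dilution of the planned difference.

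**Cost.** SAP wording and one derivation from dates already recorded. For early visits the endpoint week ends up to three days sooner. With a Day 82 visit and same-day dose it is Days 75–81, which shares Days 75–77 with Week 11. Under SAP 7.2 the MMRM uses Weeks 1, 2, 4, 8 and 12, so Week 11 enters only the imputation model. Late catch-up UENS values are not used.

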### **9.4 Pre-Treatment/Baseline Visit (Day 1)**

On Day 1, a final determination of study eligibility will be completed and placebo lead-in accountability will be performed. The diary will apply the pain eligibility algorithm to the stored data to determine if the patient is qualified. Additionally, placebo accountability will be performed for eligibility. Patients who meet the pain eligibility and placebo accountability requirement, and continue to meet all other eligibility criteria, will proceed to randomization and treatment.

The following Pre-Treatment assessments will be completed prior to randomization:

- Record medical history;
- Record prior medications;
- Administer C-SSRS (Since Last Visit version);

- Obtain vital signs (temperature, respiration rate, pulse, and blood pressure) while patient is sitting after a minimum 5-minute rest. Standing pulse and blood pressure to be obtained following sitting vital signs;
- Perform directed physical exam to assess changes from the prior visit or new concerns;
- Assess skin integrity and wound healing, if applicable;
- Perform 12-lead ECG (after the patient has been resting in the supine position);
- Collect blood samples for the following:
  - Fasting chemistry (fasting of 8-10 hours) and hematology;
- Collect urine samples for the following:
  - Urinalysis;
  - Urine pregnancy test (if FOCBP);
  - Urine drug screen (performed at the discretion of the Investigator);
- Administer BPI-SF (pain interference section only);
- Administer NTSS-6;
- Perform UENS;
- Administer Norfolk Diabetic QOL-DN; and
- Perform intraepidermal nerve biopsy (eligible patients at selected sites).

Once all Pre-Treatment assessments have been completed, the patient will be randomized using the IRT. After randomization, the following will occur:

- Dispense study drug kit assigned by IRT. The patient will be shown how to take the first dose, which will be administered at the site.
- Perform 12-lead ECG (after the patient has been resting in the supine position) one hour (+/- 10 minutes) post-dose.
- Assess for post-dosing AEs.
- Instruct patient on daily completion of NRS (worst and average pain experienced each day) and rescue medication use.

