#### **10.3.4 Key Secondary Outcome Measures**

The key secondary outcome measures are the change from baseline in the mean NRS score at Week 4 and the change in non-pain neuropathic signs and symptoms after 12 weeks as assessed by change in the UENS.

For the first outcome of the change from baseline in the mean NRS score at Week 4, the analysis approach will be identical to that for the primary outcome, with the outcome consisting of the Week 1 through Week 4 average NRS measures. The result will be obtained from the MMRM model that is fit for the primary analysis. The estimated difference in the change from baseline between the treated and placebo groups at Week 4 will be computed as part of the primary analysis. This outcome will only be formally tested if the p-value associated with the primary

outcome is less than 0.05. If the p-value associated with the primary outcome is not statistically significant, a nominal p-value for the key secondary outcome will be presented.

The second endpoint of the change in the UENS from baseline to Week 12 will be formally tested only if the p-value associated with the key secondary outcome of change from baseline in mean NRS score at Week 4 is statistically significant. To assess this outcome, an ANCOVA model will be fit including the change from baseline in UENS at Week 12 as the outcome and baseline UENS score, treatment group, and use of concomitant medication for painful DPN (yes vs. no) as covariates.

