#### **3.2. Study population**

This study will enroll patients at up to 50 sites in the United States. Patients with Type 1 or Type 2 diabetes suffering from painful distal symmetric sensorimotor polyneuropathy (painful DPN) present for  $\geq 6$  months who meet all inclusion and exclusion criteria are eligible to participate. Eligible patients will be randomized in a 1:1 ratio to receive either ricolinostat or placebo.

Exhibit 1 and Exhibit 2 display the study's inclusion and exclusion criteria, respectively.

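### The Screening UENS is collected before randomisation but used in no analysis; adding it as a second, separate covariate could sharpen the Week 12 UENS comparison at almost no cost

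*SAP*

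**What the plan says.** UENS is on the Screening list (Protocol 9.2.1). It is also on the Day 1 list, introduced by "The following Pre-Treatment assessments will be completed prior to randomization" (Protocol 9.4). The schedules in Protocol Table 1 and SAP Exhibit 3 agree.

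For every assessment other than the pain score, SAP 6.1.3 states: "For all other assessments, the baseline assessment is the last value for that assessment collected prior to randomization".

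The two documents model UENS differently, but each has a single baseline UENS term:

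- Protocol 10.3.4: "an ANCOVA model will be fit including the change from baseline in UENS at Week 12 as the outcome", adjusted for baseline UENS, treatment and concomitant pain medication.
- SAP 8.1: the repeated-measures model with multiple imputation from Section 7. That model (SAP 7.2) has one baseline term and its interaction with visit. SAP Section 1 says the SAP governs where the two differ.

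The only stated use of the Screening score is the exclusion of patients scoring above 24. It would become the baseline only if the Day 1 score were missing.

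**The concern.** A single examiner-rated sensory examination contains measurement error. A second examination made before randomisation can absorb some of it in the model, without a further visit.

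UENS is a reasonable place to want this. It is the last step of the fixed testing sequence and the only alpha-controlled test of non-pain signs. In the double-blind period it is measured once after baseline, at Week 12, so no intermediate visit adds information. It is also an in-clinic-only procedure (Protocol 13.2), so Week 12 values can be lost and the SAP imputes them. Screening and Day 1 must take place in clinic, so both pre-treatment scores should be nearly complete and available as predictors.

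Elsewhere the plan does pool repeated pre-treatment data. The pain baseline is a multi-day mean, and the QTcF confirmation rule in Protocol 11.10.2.2 averages the Screening and baseline values.

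**Working it through.** **1. The plan's own figure.** SAP 6.1.1 sets the target at 274 evaluable patients. Its inputs are 80% power, a pain-score difference of 0.8 points and an SD of 2.35, which is an effect of about 0.34 SD. Allocation is 1:1 (SAP 3.2) and alpha is two-sided 0.05 (SAP 6.1.3). Patients per arm = 2 × (1.96 + 0.8416)² × 2.35² / 0.8² = 135.5, so 136 per arm, or 272. With the noncentral t distribution, 80% is first reached at 137 per arm, or 274. The figure reproduces. It concerns the pain score; no power or precision is stated for UENS.

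**2. Inputs for UENS.** The documents give no SD, reliability coefficient or correlation, so these are assumptions:

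- r: correlation of Screening with Day 1
- b: correlation of Day 1 with Week 12
- s: correlation of Screening with Week 12

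Variances are in units of a UENS variance taken as equal at all three times, with complete Week 12 data. With one post-baseline visit in the double-blind period, the repeated-measures model reduces to ANCOVA, so the same formulas serve both documents.

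**3. Formulas.**

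- Day 1 only: 1 − b²
- Both scores as separate covariates: 1 − (b² + s² − 2bsr)/(1 − r²). If b = s = ρ, this is 1 − 2ρ²/(1 + r).
- Mean of the two as the only covariate, change still from Day 1 (b = s = ρ): 1 − 2ρ²/(1 + r) + (1 − r)/2

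**4. Both scores equally predictive.**

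| r | ρ | Day 1 only | Both, separate | Difference | Mean only | Difference |
|---|---|---|---|---|---|---|
| 0.80 | 0.6 | 0.640 | 0.600 | −6.3% | 0.700 | +9.4% |
| 0.80 | 0.7 | 0.510 | 0.456 | −10.7% | 0.556 | +8.9% |
| 0.80 | 0.8 | 0.360 | 0.289 | −19.8% | 0.389 | +8.0% |
| 0.90 | 0.6 | 0.640 | 0.621 | −3.0% | 0.671 | +4.9% |
| 0.90 | 0.7 | 0.510 | 0.484 | −5.1% | 0.534 | +4.7% |
| 0.90 | 0.8 | 0.360 | 0.326 | −9.4% | 0.376 | +4.5% |

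The mean does worse than the current plan in every row. Day 1 measurement error stays in the change score and is no longer fully adjusted for.

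**5. Screening less predictive than Day 1.** Screening is 14 to 45 days before planned randomisation (Protocol 7.1), so s may be below b. With b = 0.7 and r = 0.8:

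- s = 0.65: (0.49 + 0.4225 − 0.728)/0.36 = 0.5125; residual 0.4875 against 0.510, about 4% lower
- s = 0.60: 0.178/0.36 = 0.4944; residual 0.5056, about 1% lower
- s = 0.56: 0.1764/0.36 = 0.49; residual 0.510, no gain, because s = b × r

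**6. What this is worth.** Sample-size equivalent = 1/ratio. A ratio of 0.893 equals 12% more patients (274/0.893 = 307), and 0.802 equals 25% (341). An effect with 80% power on Day 1 alone at 137 per arm would have power Φ(2.80/√ratio − 1.96): 84% and 88% respectively, and 80% where nothing is gained.

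**7. Validity.** A simulation of 3,000 trials per setting (274 patients, all three correlations equal at 0.5 or 0.7) was run with and without removing patients whose Screening score lay more than one SD above the mean, to mimic the eligibility cap. With both covariates, bias was about zero and type I error was 0.044 to 0.053. Variance ratios were 0.898 and 0.858 without the cap, and 0.915 and 0.882 with it, so a cap trims the gain slightly. These ratios carry simulation error; the sizes above come from the formulas.

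**The case against.** The best case for leaving the plan alone has four parts.

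- **The rule is sound.** The last value before dosing is a standard, unbiased baseline, and the models already adjust for it. This stands in full. A reader might infer that the SAP has made an error or biased the UENS comparison; the documents do not support that. Nothing in the rule is contradictory or undefined.
- **The gain cannot be shown from the documents.** This also stands. A reader might take 3% to 25% more patients (the span for r 0.80 to 0.90 and ρ 0.6 to 0.8) as assured. That span requires Screening to predict Week 12 as well as Day 1 does, and step 5 shows the lower end is about zero. SAP 4.2.5 describes UENS as highly reproducible without a figure. If the two scores correlate 0.95, with 0.7 to Week 12, the reduction is only 2.5%.
- **The reach is limited.** UENS is formally tested only after both pain tests succeed. It is also not the only look at non-pain features, since the NTSS-6 covers numbness and tingling as an uncontrolled secondary endpoint. Both points stand, although a narrower interval is useful whatever the pain results.
- **Averaging seems just as good.** It is not, if change is still taken from Day 1. Taking both the change and the covariate from the mean would recover the gain, but it redefines the UENS baseline. Separate covariates avoid that.

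None of this argues against separate covariates. Their cost is one degree of freedom in about 274 patients.

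**Conclusion.** The point holds as a free improvement, not as a correction. Two pre-randomisation UENS scores exist and the planned analyses use one. Entering both separately leaves the treatment comparison unbiased and, apart from one degree of freedom, cannot lose precision.

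The expected benefit is about 0% to 20% lower residual variance, or 0 to about 8 power points for an effect that would otherwise have 80% power. This rests on assumed correlations, equal variances and complete Week 12 data. The range describes the values examined and is not a bound. Where the trial falls in it depends mainly on whether Screening predicts Week 12 beyond what Day 1 already explains.

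**What to change.** 1. Keep change from Day 1 to Week 12 as the UENS outcome.
2. In the SAP 8.1 UENS model, which governs, enter Screening UENS and Day 1 UENS as two separate covariates. If the model is fitted with more than one post-baseline visit, give each its own interaction with visit. Make the same change to the Protocol 10.3.4 ANCOVA if that model is retained.
3. Include both scores in the UENS imputation model.
4. State that the mean of the two will not be used as the sole covariate alongside change from Day 1.
5. Say how a patient with only one pre-treatment score is handled, since the last-value rule would then make Screening the baseline.
6. Fix this before unblinding. The blinded data review in SAP 5.1 is a suitable point, and the pooled correlations can be inspected there without treatment codes.

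**Cost:** a short SAP amendment, one extra model term, and no new visit or examination.
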